Assignment of SID number and randomization		X ^c										
Record vital signs	X ^d	X ^e	X ^f			X		X ^{e,f}			X	
Investigational product administration												
Full informed consent, if not done at screening, for Dose 2 and procedures on or after Day 3						X						
Full medical history review						X						
Physical examination (full)						X					X	

Table 8 Treatment Period and Follow-up Procedures: Cohort A (Red Regimen)

Study Period	Treatment Period										Follow-up	
Visit Number	V1 (Inpatient)							V2	V3	V4	V5	V6
Procedure / Study Day	Day 1					Anytime between Days 1-3	Day 3 (48 ± 8 hours)	Day 10 (±1 day) Phone	Day 17 (± 1 day)	Day 24 (± 1 day) Phone	Day 31 (± 1 day)	Days 70-84 ^a
	Screening	Pre-PCI										
Assess for infusion site reaction												
Assessment of AEs/SAEs ¹		X	X					X	X	X	X	X
Post-dose observation ^j												
Concomitant medications	X	X ^c	X					X	X	X	X	X
Weight							X					X
Height							X					
12-lead ECG												X
Serum chemistry, creatinine ^k , GLDH, CK and troponin		X ^c					X ^e		X		X	X
Hematology, cystatin C, NT-proBNP		X ^c					X ^e					X
PK blood sample		X ^c	X ^l				X ^{e,f}		X		X	X
PD blood sample		X ^c		X ^m			X ^{e,m}		X ^m		X ^m	X ^m
Immunogenicity blood sample		X ^c							X		X	X
LH/FSH							X					

Table 8 Treatment Period and Follow-up Procedures: Cohort A [REDACTED] Regimen)

Study Period	Treatment Period										Follow-up	
Visit Number	V1 (Inpatient)							V2	V3	V4	V5	V6
Procedure / Study Day	Day 1					Anytime between Days 1-3	Day 3 (48 ± 8 hours)	Day 10 (±1 day) Phone	Day 17 (± 1 day) Phone	Day 24 (± 1 day) Phone	Day 31 (± 1 day) Phone	Days 70-84 ^a
	Screening	Pre-PCI	[REDACTED]	[REDACTED]	[REDACTED]							
Future use blood sample, if consented ⁿ		X ^c					X ^{e,m}					X ^m
Verify additional procedure requirements for CMR imaging (10-12 week [70-84 days post Dose 1] follow-up imaging)												X
CMR												X ^o

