AE = adverse event; CCU = cardiac care unit; CK = creatine kinase; CK-MB = creatine kinase-MB; CMR = cardiovascular magnetic resonance (imaging); COVID-19 = coronavirus disease; CTA = computed tomography angiography; ECG = electrocardiogram; eCRF = electronic case report form; FSH = follicle-stimulating hormone; GLDH = glutamate dehydrogenase; LH = luteinizing hormone; NT-proBNP = N-terminal pro b-type natriuretic peptide; PCI = percutaneous coronary intervention; PD = pharmacodynamic; PK = pharmacokinetic; SAE = serious adverse event; SID = subject identification; TIMI = Thrombolysis in Myocardial Infarction; V = visit

^a See Section 4.2.1.1 for COVID-19 permissible modifications.

^b Only if diagnostic ECG not of sufficient quality

^c Within 2 hours prior to PCI [REDACTED]

^d Where applicable for the screening vital signs, the vital signs taken as part of standard of care can be used if taken within 30 minutes [REDACTED] due to the acute nature of the study. The screening vital signs assessments and the [REDACTED] vital signs assessments do not need to be duplicated as long as one assessment is made within 30 minutes prior to [REDACTED]. If the [REDACTED] vital signs measurements are more than 30 minutes prior to [REDACTED] these must be repeated.

^e [REDACTED]

^f 10 minutes (± 5 minutes) [REDACTED]

Table 8 Treatment Period and Follow-up Procedures: Cohort A [REDACTED] Regimen)

Study Period	Treatment Period									Follow-up		
Visit Number	V1 (Inpatient)						V2	V3	V4	V5	V6	
Procedure / Study Day	Day 1					Anytime between Days 1-3	Day 3 (48 ± 8 hours)	Day 10 (±1 day) Phone	Day 17 (± 1 day) Phone	Day 24 (± 1 day) Phone	Day 31 (± 1 day) Phone	Days 70-84 ^a
	Screening	Pre-PCI and Dose 1	Immediately Post-Dose/PCI	1-1.5 hr Post-Dose	12-18 hr Post-Dose							

^g Should be prior to PCI, preferably >10 minutes prior

^h Visits or missed doses that will potentially fall outside of the window specified in this table must be discussed with the TIMI Hotline as early as possible in order to adjust visit/dosing schedule.

ⁱ AE collection begins after randomization and lasts until the end of the study. SAE collection begins after the subject signs the informed consent document and lasts until the end of the study.

^j For [REDACTED] observation, subjects will be monitored for 2 hours in a location with personnel trained in Adult Advanced Life Support with proper resuscitation equipment available.

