4.8.3.4 Exploratory Analyses

The exploratory objectives are to determine whether MEDI6012

█

Incidence of CV death or heart failure and incidence of CV death, MI, unstable angina or urgent coronary revascularization from randomization to final study visit (10-12 weeks post-randomization) will be calculated. Time to first major adverse CV event will be analyzed using log-rank test.

The proportion of TFG at baseline (on initial angiography, pre-PCI) and the proportion of subjects with decline in renal functions at 48 hours will be compared between MEDI6012 and placebo using chi-square test.

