4.8.4.2 Analysis of Clinical Laboratory Parameters

Clinical laboratory safety tests including serum chemistry and hematology parameters will be summarized using descriptive statistics at each time point by treatment group with placebo group combined when appropriate. Change from baseline to each post baseline time point in these data will also be summarized, where appropriate. A shift table will be provided for these clinical laboratory parameters as well where possible.

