2.1.3 Exploratory Study Objectives

Exploratory objectives and associated endpoints are presented in Table 2.3.

Table 2.3 Exploratory Objectives and Associated Endpoints

Type	Objective	Endpoint(s)
Biomarker	To determine whether MEDI6012 [REDACTED]	[REDACTED]
Biomarker	To evaluate the effect of MEDI6012 [REDACTED]	[REDACTED]
Safety	To evaluate the effect of MEDI6012 [REDACTED]	[REDACTED]
Efficacy	To evaluate the effect of MEDI6012 [REDACTED]	[REDACTED]
Efficacy	To evaluate the effect of MEDI6012 on [REDACTED] in serum creatinine of ≥ 0.5 mg/dL (≥ 44 μ mol/L)	[REDACTED]

CTA = computed tomography angiography; CV = cardiovascular; MI = myocardial infarction; pPCI = primary percutaneous coronary intervention; TFG = TIMI flow grade; TIMI = thrombolysis in myocardial infarction.

[figure not shown]

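### In the readable text, 48-hour renal function is compared between arms only as a proportion by chi-square; a baseline-adjusted analysis of the creatinine already collected should be added alongside it.

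*Protocol*

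**What the plan says.** Protocol 4.8.3.4, Exploratory Analyses, gives the test: "the proportion of subjects with decline in renal functions at 48 hours will be compared between MEDI6012 and placebo using chi-square test". No covariate or analysis population is named.

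SAP 2.1.3, Table 2.3, lists an objective of type Efficacy whose readable part is "in serum creatinine of ≥ 0.5 mg/dL" (44 μmol/L). The words before this fragment and the endpoint cell are redacted.

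The data for a full-scale analysis are scheduled. Protocol Tables 8 and 9 carry the row "Serum chemistry, creatinine ^k , GLDH, CK and troponin" for Cohorts A and B, marked before PCI and on Day 3. The footnote to the first sample reads "Within 2 hours prior to PCI"; the second column is headed "Day 3 (48 ± 8 hours").

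The other readable use of creatinine is the safety laboratory summary. Protocol 4.8.4.2 says "Change from baseline to each post baseline time point in these data will also be summarized, where appropriate", by treatment group, with a shift table. SAP 3.6.4 says the same. Neither plans a between-arm estimate or test.

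SAP 3.1 sets all tests one-sided at 0.05 unless stated otherwise and calls for one-sided confidence intervals.

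**The concern.** Serum creatinine is continuous and is measured twice in each subject, about 48 hours apart. Reducing the pair to whether a threshold was crossed discards most of the information when few subjects cross it. Protocol 4.1.3 excludes known chronic renal impairment and known creatinine clearance of 30 mL/min or less, so a rise of 0.5 mg/dL in two days is plausibly uncommon, although the documents do not say how uncommon.

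What is at stake is the interpretation of an exploratory result. With few events, a non-significant chi-square says little about whether creatinine moved between the arms. The samples that could say more are already planned. The primary endpoint and the main conclusions are not affected.

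**Working it through.** **The plan's own figures.** The documents give no rate, SD, effect or power for the renal endpoint, so there is no renal figure to reproduce. The sample sizes can be checked:
- 90 evaluable per arm with 50% exclusion (SAP 4): 90 / (1 − 0.5) = 180 per arm, as Protocol 4.8.2 states.
- 540 × 0.5 × 0.6 = 162, the second interim size in Protocol 4.8.8.

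Two MEDI6012 arms of about 180 and two placebo groups of about 90 (Protocol 3.1.2) give 360 against 180.

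**Assumptions not in the documents.** The placebo event rate p0, the odds ratio OR, and a change in creatinine that is normally distributed with the drug shifting every subject equally.

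**Formulas.**
1. Event rate on MEDI6012: p1 = OR·p0 / (1 − p0 + OR·p0).
2. Shift in SD units that produces p1 at the same cut: d = z(1 − p1) − z(1 − p0).
3. Full-scale power: non-central t with 538 degrees of freedom and non-centrality d·√(360 × 180 / 540) = d × 10.95. This is an unadjusted comparison of change; baseline adjustment could only be expected to help.
4. Cut power: simulated binomial counts, uncorrected chi-square. The one-sided version uses its signed root.

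**Example, p0 = 5%, OR = 0.5.** p1 = 0.025 / 0.975 = 2.56%. d = 1.949 − 1.645 = 0.304. Non-centrality = 0.304 × 10.95 = 3.33. Expected events: 360 × 0.0256 + 180 × 0.05 = 9.2 + 9.0 = 18.2 among 540 subjects.

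**Results, OR = 0.5, cut against full scale.**

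| p0 | p1 | d (SD) | Expected events | One-sided 0.05 | Two-sided 0.05 |
|---|---|---|---|---|---|
| 3% | 1.52% | 0.28 | 10.9 | 33% vs 93% | 22% vs 87% |
| 5% | 2.56% | 0.30 | 18.2 | 44% vs 95% | 33% vs 91% |
| 10% | 5.26% | 0.34 | 36.9 | 65% vs 98% | 54% vs 96% |
| 15% | 8.11% | 0.36 | 56.2 | 78% vs 99% | 68% vs 98% |
| 20% | 11.11% | 0.38 | 76.0 | 86% vs 99% | 79% vs 99% |

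For OR = 0.67 at p0 of 3, 5 and 10%, one-sided power is 19% vs 57%, 24% vs 62% and 35% vs 71%. Both analyses are weaker, and the gap remains.

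**Sensitivity checks.**
- *Missing samples.* With 15% missing (306 against 153) and OR 0.5, the one-sided figures at 3, 5 and 10% are 30% vs 89%, 40% vs 92% and 59% vs 96%.
- *Shift fixed at 80% full-scale power.* Over 360 against 180 and 180 against 180, one- and two-sided, and both directions, the cut has 13 to 24% power at a placebo rate of 2%, 22 to 35% at 5%, 32 to 46% at 10%, 40 to 52% at 15% and 46 to 56% at 20%.
- *Simulated ANCOVA.* This used 360 against 180, one-sided 0.05, 3,000 runs per scenario, an assumed baseline median of 0.95 mg/dL and a log-SD of 0.25. With falls of 0.05, 0.065 and 0.08 mg/dL and SD of change 0.20, 0.25 and 0.30, ANCOVA has 87, 89 and 90% power and the cut 23, 31 and 43%.
- *Wider definition.* If a 25% relative rise also counted as decline (an assumption), chi-square would have 54, 61 and 66% in those three cases.
- *Effect confined to large rises.* If 10% of placebo and 5% of MEDI6012 subjects have a large rise (mean 0.8 mg/dL) and nobody else shifts, chi-square has 61% and ANCOVA 54%. With 5% against 2.5%, two-sided, the figures are 32% for the cut and 22% for the full scale.

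**The case against.** Four objections carry weight.

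**Redaction.** A reader might infer that creatinine is tested nowhere except through this cut. The documents do not support that. The body of SAP 3.4.3, Other Efficacy Analyses, is absent from the public copy, and Protocol Table 5 and parts of SAP Table 2.3 are blacked out. A full-scale analysis could be specified there, and the definition of decline could be wider than the visible fragment. The point is therefore limited to readable text.

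**Size.** A reader might also infer that a shift is mostly missed. That holds only for a uniform shift, an uncommon event and the 0.5 mg/dL cut alone. At a 10% rate with the odds halved, the cut already has 65% one-sided power. At OR 0.67 even the full-scale analysis reaches only 57 to 71% over rates of 3 to 10%.

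**Mechanism.** The documents favour neither a general shift nor an effect confined to large rises, and in the second case the cut does better. This stands, and it rules out replacing the chi-square test with a model.

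**Importance.** The endpoint is exploratory, p-values are nominal, and no readable decision rule depends on it. The proportion with a clinically sized decline also answers a different question from a small mean shift. No passage says that a non-significant result would be read as absence of a renal effect; that is only a possible misreading.

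The descriptive summaries answer part of the point, because a crude difference could be derived from them. They do not supply a planned, baseline-adjusted estimate with an interval.

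**Conclusion.** The point holds as a minor, optional improvement. In the readable text, paired continuous creatinine is collected in both cohorts and the only between-arm analysis of 48-hour renal function is a chi-square on a proportion.

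Under the stated assumptions (uniform normal shift, placebo rate 3 to 10%, odds ratio 0.5, 360 against 180, one-sided 0.05), power is about 33 to 65% for the cut and 93 to 98% on the full scale. The direction of the gap does not depend on sidedness or on 15% missing data. Its size does depend on the event rate, the redacted definition and the form of the effect. The split of 360 to 180 is the planned one; Protocol 4.2.1.1 moves later randomization to 1:1 in Cohort B, so the final split will be somewhat more even.

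**What to change.** In Protocol 4.8.3.4 and the SAP's exploratory efficacy section:
- Keep the proportion with renal decline and its chi-square comparison.
- Unless the redacted text already does so, add alongside it an ANCOVA of log Day 3 serum creatinine on log pre-PCI serum creatinine and treatment. Report the geometric mean ratio of MEDI6012 to placebo with its confidence interval. SAP 3.4.1.3 already uses this scale for infarct size.
- State the analysis population for both analyses, and apply the plan's stated sidedness to both.

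The cost is a few lines of SAP text and one model on data already collected, with no new samples, visits or subjects. The downside is one more exploratory result, on a scale that is less directly clinical than the proportion.

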4.8.4 Safety

4.8.4.1 Analysis of Adverse Events

Safety analysis will be based on the As-treated Population. AE collection begins after randomization and lasts until the end of the study. SAE collection begins after the subject signs the informed consent document and lasts until the end of the study. Adverse events will be coded using the Medical Dictionary for Regulatory Activities (MedDRA) by SOC and PT. Specific AEs will be counted once for each subject for calculating rates, but will be presented in total in subject listings. In addition, if the same AE occurs multiple times within a particular subject, the highest severity and level of causality will be reported. All TEAEs will be summarized overall and by MedDRA SOC and PT, by severity and relationship to investigational product. In addition, summaries of deaths, SAEs and treatment discontinuations due to AEs will be provided.

4.8.4.2 Analysis of Clinical Laboratory Parameters

Clinical laboratory safety tests including serum chemistry and hematology parameters will be summarized using descriptive statistics at each time point by treatment group with placebo group combined when appropriate. Change from baseline to each post baseline time point in these data will also be summarized, where appropriate. A shift table will be provided for these clinical laboratory parameters as well where possible.

4.8.4.3 Other Safety Analyses

Vital sign results will be summarized using descriptive statistics at each time point by treatment group.

4.8.5 Analysis of Immunogenicity/Pharmacokinetics

ADA incidence rate and titer will be tabulated for each treatment group. Samples confirmed positive for ADA will be tested and analyzed for nAb and summarized similarly.

Serum MEDI6012 mass concentration-time profiles will be summarized for MEDI6012 treated subjects by dose cohort by visit.

Additional PK analyses may be conducted as appropriate. Data obtained in this study may be pooled with other MEDI6012 studies to perform population PK analysis and/or PK/PD analysis.

4.8.6 Analysis of Pharmacodynamic Parameters

The following PD markers will be collected:

The PD markers measured at each time point and change from baseline each post baseline time point will be summarized using descriptive statistics by treatment group with placebo group combined when appropriate.

4.8.7 Data Monitoring Committee

An independent DMC will be appointed. The DMC will be responsible for safeguarding the interests of the patients, by assessing the safety of the intervention during the study and for reviewing the overall conduct of the study. The DMC will have access to the individual treatment codes and will be able to merge these with the collected study data while the study is ongoing. DMC will review prespecified data periodically to ensure subject safety and make recommendations to the sponsor regarding further conduct of the study. This recommendation will be relayed to the MedImmune safety review committee and appropriate action will be taken. The DMC will have scheduled meetings at study initiation and at the following enrollment milestones – 15%, 30%, and 60% enrollment achieved. In addition, the DMC chairman will receive data once every two months and may schedule *ad hoc* meetings at his/her discretion. A separate charter will establish the rules, meeting frequency and scope of responsibilities of the DMC.

4.8.8 Interim Analysis

█ interim analyses are planned. The objective of the █ interim analysis will be for futility and potentially dropping a dose regimen. It will be conducted after 30% of the initially planned Primary Efficacy Analysis Population (N = 74) is enrolled and will require that > 50% of subjects (N > 37) have acute anterior STEMI and have completed their final study visit. The █ interim analysis will be conducted through Data Monitoring Committee with details in the DMC charter. The █ interim analysis is planned to accelerate decision on future development options for MEDI6012 and will be performed once 60% of the revised Primary Efficacy Analysis Population (N = 162) is enrolled and will require that > 50% of subjects (N > 81) have acute anterior STEMI and have completed their final study visit. Details of the second interim analyses will be specified in the interim analysis plan. The

sponsor and Principal Investigator will monitor the statistical assumptions in a blinded fashion and decide the exact time for interim analyses.

5 ASSESSMENT OF SAFETY

5.1 Safety Monitoring

The details of safety monitoring will be detailed in the safety monitoring plan. Safety monitoring will be performed by the principal investigator, sponsor medical monitor in consultation with the global safety physician, TIMI safety desk and the DMC.

The principal investigator is responsible for monitoring enrolled subjects for safety findings, including the recording in the eCRF (RAVE) of AEs, SAEs, and appropriate reporting, communication, and follow-up of laboratory abnormalities. The TIMI hotline is staffed by TIMI study physicians and will be available 24 hours per day, 7 days per week for protocol and safety related questions and concerns. When an SAE is entered into the eCRF, the TIMI safety desk, medical monitor, and global safety physician will be notified. The TIMI hotline and TIMI safety desk will be responsible for documenting protocol and safety related issue communications with PIs and communicating significant findings to MedImmune and the sponsor medical monitor. When an SAE is documented in the clinical database (RAVE), the TIMI safety desk will submit queries within 24 hours confirming seriousness, causality, and further details regarding the SAE to facilitate whether further information is needed. These assessments will be made urgently in order to comply with the timeframes for reporting to regulatory authorities. The investigator is required to respond to these queries within 24 hours.

SAEs will be reviewed by the sponsor medical monitor, in consultation and with the global safety physician, and further queries issued, if necessary. If there is no evidence for the designation of an event as serious (in line with the appropriate protocol definition) or there is no apparent evidence for the positive investigator causality assessment, TIMI and the sponsor medical monitor may query or discuss with the investigator. However, if agreement is not reached, the investigator assessment will be respected and not changed by TIMI or MedImmune. The same is true if there is evidence to suggest a positive causality assessment for an SAE that has been assessed as unrelated by the investigator.

SAE reconciliation between the safety database (Sapphire) and the clinical study database will be performed on a monthly basis by TIMI and reviewed by the global study physician and medical monitor via monthly meetings.

The details of safety monitoring will be detailed in the Safety Monitoring Plan.

5.2 Definition of Adverse Events

The ICH Guideline for Good Clinical Practice E6(R1) defines an AE as: Any untoward medical occurrence in a patient or clinical investigation subject administered a pharmaceutical product and which does not necessarily have a causal relationship with this treatment. An AE can therefore be any unfavorable and unintended sign (including an abnormal laboratory finding), symptom, or disease temporally associated with the use of a medicinal product, whether or not considered related to the medicinal product.

An AE includes but is not limited to any clinically significant worsening of a subject's pre-existing condition. An abnormal laboratory finding (including ECG finding) that requires medical intervention by the investigator, or a finding judged by the investigator as medically significant should be reported as an AE. If clinical sequelae are associated with a laboratory abnormality, the diagnosis or medical condition should be reported (eg, renal failure, hematuria) not the laboratory abnormality (eg, elevated creatinine, urine red blood cell increased). Abnormal laboratory values that are not, in the investigator's opinion, medically significant and do not require intervention should not be reported as AEs.

AEs may be treatment emergent (ie, occurring after initial receipt of investigational product) or nontreatment emergent. A non-TEAE is any new sign or symptom, disease, or other untoward medical event that begins after written informed consent has been obtained but before the subject has received investigational product.

Elective treatment or surgery or preplanned treatment or surgery (that was scheduled prior to the subject being enrolled into the study) for a documented pre-existing condition that did not worsen from baseline is not considered an AE (serious or nonserious). An untoward medical event occurring during the prescheduled elective procedure or routinely scheduled treatment should be recorded as an AE or SAE.

5.3 Definition of Serious Adverse Events

An SAE is any AE that:

- Results in death
- Is immediately life-threatening
- Requires inpatient hospitalization or prolongation of existing hospitalization
- Results in persistent or significant disability/incapacity
- Is a congenital anomaly/birth defect in offspring of the subject
- Is an important medical event that may jeopardize the subject or may require medical intervention to prevent one of the outcomes listed above

Medical or scientific judgment should be exercised in deciding whether expedited reporting is appropriate in this situation. Examples of medically important events are intensive treatment in an emergency room or at home for allergic bronchospasm, blood dyscrasias, or convulsions that do not result in hospitalizations; or development of drug dependency or drug abuse.

